1.7. MODIFICATIONS FROM THE APPROVED STATISTICAL ANALYSIS PLAN

Approved SAP (V1.0 of 23OCT2019)	Modification
Section 1.7: “an interim analysis has been performed with all screened patients who have met all the eligibility criteria and who have received the treatment at baseline visit (D1).”	“an interim analysis has been performed with all screened patients who have met all the eligibility criteria and who have received the treatment at baseline visit (D1)”
Section 5.1.5.3: “Patients’ profiles will be explored using the same analyses performed for the interim analysis”	“Patients’ profiles will be explored using the same analyses performed for the interim analysis of baseline data”
Section 7 : ” Interim analysis details have been presented in a separate document (SANOFI - SARIPRO- Statistical Analysis Plan - INTERIM ANALYSIS Version 2.0 20190611).”	Interim analysis details An analysis of baseline data have been presented in a separate document (SANOFI - SARIPRO- Statistical Analysis Plan - INTERIM ANALYSIS Version 2.0 20190611).

^D See Appendix A: Derived data

2. COLLECTED DATA

2.1. SITE QUESTIONNAIRE

Not applicable.

2.2. SCREENING LOG

A screening log form has been provided for each site. All screened patients have been registered on the screening log form with the following information:

- Date of visit (DD/MM/YYYY)
- Patient number (if enrolled)
- Reason for non-enrolment into the registry
 - Non-compliance with inclusion/ exclusion criteria
 - Patient's refusal of consent.

2.3. PATIENT DATA

Data collected on patients during the study are about:

- Eligibility criteria
- Demography
- Vital signs and physical exam
- Medical (Medical and surgical history in relation with RA, medical history and associated diseases)
- Characteristics of RA
- RA activity
- Laboratory tests
- Investigational Medicinal Product (IMP) administration
- Concomitant treatments
- PROs questionnaires
- Adverse Events (AEs)

Collected data will be presented more precisely below.

3. GENERAL STATISTICAL APPROACH

3.1. DESCRIPTIVE STATISTICS

Each modality of qualitative data will be presented with their number, percentage and 95% CI will also be presented.

For quantitative data, mean, median, minimum and maximum as well as standard deviation , interquartile range and 95% CI will be described.

For all the variables, number of available and missing observations will be specified.

Data will be presented using an appropriate number of decimal places (i.e. the number of decimal places used does not imply undue precision):

- Raw data : same number of decimal as collected,
- Derived data: The appropriate number of decimal places will be determined by general practice, mathematical rationale or scientific rationale (e.g. age should be presented in whole numbers),
- Mean, median and standard deviation : reported to one decimal place greater than the raw/derived data that they summarise,
- Minimum and maximum : same precision as the raw data,
- Percentage : one decimal place,
- P-values : four decimal places (e.g.: $p=0.0037$), after rounding. P-values which are less than 0.0001 will be presented as '<0.0001'.

3.2. ANALYSIS SETS

3.2.1. Enrolled patients

All patients screened, who have signed the Informed Consent Form (ICF) and who never took the study treatment at any time before baseline.

3.2.2. Intent-to-treat population (ITT)

All patients included (i.e. for whom the inclusion decision “Has the decision to include the patient been taken” is ‘Yes’) and who took the treatment at least once.

3.2.3. Per Protocol Set (PPS)

3.2.4. Patients of ITT population without major protocol deviations as defined during the Data Review meeting and who are evaluable for the main criterion. **Safety population (SAF)**

All patients who have signed the Informed Consent Form (ICF) and have been exposed to at least one dose or part of a dose of investigational medicine product (IMP).

4. ANALYSIS OF SITE QUESTIONNAIRE

Not applicable.

5. ANALYSIS OF PATIENT DATA

5.1. ANALYSIS VARIABLES

5.1.1. Patients' characteristics

- **Demography**

- Age at baseline (years)
- Sex (Female / Male)

- **Physical examination and vital signs at baseline**

- Height (cm)
- Weight (kg)
- Body Mass Index (BMI)^{DD} (kg/m²)
 - As quantitative
 - In classes:
 - Underweight (<18.5)
 - Normal (healthy) weight ([18.5; 25[)
 - Overweight ([25.0; 30[)
 - Obese (≥30)
- Abdominal girth (cm)
- Blood pressure
 - Systolic (mmHg)
 - Diastolic (mmHg)
- Heart rate (beats/min)

- **Medical and surgical history**

- Medication history for rheumatoid arthritis

- Time from RA diagnosis (years)^{DD}
- Patient previously treated with conventional synthetic DMARDs (Yes/No)
- Patients previously treated with biological therapies and targeted synthetic DMARDs at baseline (Yes/No)
- Patients previously treated with corticosteroids (Yes/No)
- Patient currently treated with NSAIDs, analgesics (Yes/No)
- Patient currently receiving other treatments for their RA (Yes/No)
- Patient treated with other treatment (other than those for RA) (Yes/No)

Conventional synthetic DMARDs, biological therapies and targeted synthetic DMARDs, corticosteroids and NSAIDs, analgesics will be presented according to their status at baseline: ongoing or ended at baseline.

- Medical history and associated diseases

- Patient having experienced any past or concomitant diseases (clinically significant) (Yes/No)

If yes, past or concomitant diseases will be presented by System Organ Class (SOC) and Preferred Term (PT).

➤ Surgical history in relation with rheumatoid arthritis

- Patient having any surgical history in relation with rheumatoid arthritis (Yes/No)
If yes, surgical history will be presented by SOC and PT.

- **Characteristics of rheumatoid arthritis**

- Anti-CCP (Positive/Negative/Not performed)
- Rheumatoid factor (Positive/Negative//Not performed)
- Signs of structural joint involvement (Yes/No)
- At least one rheumatoid nodule (Yes/No)
 - If yes:
 - Size of the largest nodule at screening and at the last measure (mm)
 - Changes from baseline^{DD}
 - Time between measures of the rheumatoid nodule (months)^{DD}
- Chest X-Ray (Normal or with a non-clinically-significant abnormality / Abnormal with a clinically-significant abnormality / not performed)

- **Evaluation of rheumatoid arthritis activity**

- Visual Analogue Scale (VAS) Global Assessment of disease activity (mm) by physician (0=no pain to 100-maxima pain imaginable)

- **Evaluation of the patient's feeling**

- Emotional items on a 5-Likert scale (from 0=never to 4=constantly):
 - Sadness
 - Joy
 - Irritability
 - Panic
 - Anxiety
 - Anger
 - Exaltation

- **Prior and concomitant treatments at baseline**

Only treatments with a start date prior to date of baseline will be presented.

- Subjects with at least one prior treatment (ended) at baseline
- Subjects with at least one prior treatment ongoing at baseline

Prior and concomitant treatments will be coded using World Health Organization - Drug Dictionary (WHO-DD) (current version at the time of encoding).

5.1.2. Primary endpoint (6-month core period)

Primary endpoint is the change in RAID score from baseline to W24. The RAID score ranging from 0 (best) to 10 (worst).

5.1.3. Secondary endpoints (6-month core period)

- **PROs questionnaires**

- [RAID](#) score per item and total score^{DD}
The RAID score gives a number between 0 and 10. A higher score on the RAID indicates more impact of the disease.
A score ≤ 2 out of 10 is considered a patient-acceptable status.

- Hospital Anxiety and Depression Scale ([HADS](#)):
 - Per item
 - Anxiety calculated score as quantitative^{DD} and in classes
 - Normal (0-7)
 - Borderline abnormal (8-10)
 - Abnormal (11-21)
 - Depression calculated score as quantitative^{DD} and in classes:
 - Normal (0-7)
 - Borderline abnormal (8-10)
 - Abnormal (11-21)
- Multidimensional Assessment of Thymic States ([MATHys](#))^{DD}
 - Per item
 - 5-dimension scores:
 - Emotion
 - Cognition
 - Psychomotor function
 - Motivation
 - Sensory perception
 - MATHys total score
- Functional Assessment of Chronic Illness Therapy – Fatigue ([FACIT-F](#)) per item and total score
- Health Assessment Questionnaire - Disability Index ([HAQ-DI](#)) per domain (dressing & grooming, arising, eating, walking, hygiene, reach, grip and activities) and total score.
- International Physical Activity Questionnaire ([IPAQ](#)) classification per domain and total score as quantitative and in classes:
 - Low physical activity
 - Moderate physical activity
 - High physical activity
- Patient global assessment of disease activity using a 100 mm Visual Analogue Scale (VAS)
- Duration of morning stiffness (minutes)
- **Evaluation of RA activity**
- Erythrocyte sedimentation rate (ESR) (1st hour) (mm/h)
- Number of swollen joints (SJC)
- Number of tender joints (TJC)
- DAS28-ESR^{DD}
 - Low Disease Activity (LDA) (Yes/No)
 - Remission (Yes/No)
- CDAI^{DD}
 - Low Disease Activity (LDA) (Yes/No)
 - Remission (Yes/No)

 - Patient with at least one injection performed in the abdomen (Yes/No)
 - Patient with at least one injection performed in the thigh (Yes/No)
 - Patient with at least one injection performed in another injection site (Yes/No)
A listing of other injection site will be provided.
- Place of injection
 - Patient with at least one injection performed on site (Yes/No)
 - Patient with at least one injection performed at home (Yes/No)
- Person who performed the injection
 - Patient with at least one injection performed by himself (Yes/No)
 - Patient with at least one injection performed by a healthcare professional (Yes/No)
 - Patient with at least one injection performed by another person (Yes/No)
- Problem encountered during injection
 - Patient who received at least once a smaller volume than that in the syringe (Yes/ No)
 - Patient with at least one injection done incorrectly (Yes/No)
 - Patient with at least one other problem encountered during injection (Yes/No)
A listing will be provided for other problem encountered during injection.
- Treatment compliance
 - Injection performed (Yes/No)
If yes:
 - Dose (150mg/200mg)
 - Injection site (Abdomen/Thigh/Other)
 - Place of injection (On site/At home)
 - Person who performed the injection (Patient/Healthcare professional/Other)
 - Problem encountered during injection (None/Volume injected below that of the syringe/ Injection done incorrectly/Other)
 - If no:
 - Reason (Adverse Event/ Forgetting/ Other reason)

- **Vital signs and physical examination**

- Weight (kg)
- BMI^{DD} (kg/m²)
 - As quantitative
 - In classes:
 - Underweight (<18.5)
 - Normal (healthy) weight ([18.5; 25[)
 - Overweight ([25.0; 30[)
 - Obese (≥30)
- Blood pressure
 - Systolic (mmHg)
 - Diastolic (mmHg)
- Heart rate (beats/min)
- Abdominal girth (cm)
- Electrocardiogram (ECG) result (Normal or with a non-clinically-significant abnormality / Abnormal with a clinically-significant abnormality / not performed)

- **Concomitant treatments**

Prior and concomitant treatments will be presented and coded using World Health Organization - Drug Dictionary (WHO-Drug Dictionary) (current version at the time of encoding).

5.1.5. Exploratory endpoints

5.1.5.1. Associations between changes in RAID score and composite disease activity scores (DAS28-ESR^{DD} and CDAI^{DD}).

At each visit, all the efficacy parameters will be assessed.

- DAS28-ESR^{DD} score
- CDAI^{DD} score
- RAID total score

5.1.5.2. Associations between changes in Hospital Anxiety and Depression Scale (HADS) scores and in composite disease activity scores (DAS28-ESR^{DD} and CDAI^{DD}).

At each visit, all the efficacy parameters will be assessed.

- DAS28-ESR^{DD} score
- CDAI^{DD} score
- HADS scores:
 - Anxiety calculated score
 - Depression calculated score

5.1.5.3. To explore patients' profiles

Patients' profiles will be explored using the same analyses performed for the analysis of baseline data. Association between cognitive troubles and patients' characteristics will be tested. Cognitive troubles will be evaluated by the MATHyS cognition score as qualitative variable (using the tertiles: <1st tertile, [1st tertile; 2nd tertile[, ≥ 2nd tertile).

Characteristics (at baseline) to be tested are:

- Age in quantitative or in classes (using quartiles) if linearity is not verified
- Sex (Female / Male)
- BMI in classes (Normal/Abnormal i.e Underweight or Overweight or Obese)
- Time between baseline and initial diagnosis (years) in quantitative or in classes (using quartiles), if linearity is not verified
- DAS28-ESR in quantitative or in classes (using quartiles), if linearity is not verified
- Patient previously treated with biological therapies and targeted synthetic DMARDs (Yes/No)
- Patient currently treated with corticosteroids for his/her RA (Yes/No)
- Patient currently treated with NSAIDs, analgesics (Yes/No)
- Patient having experienced any past or concomitant diseases (clinically significant) (Yes/No)
- Depression evaluated by HADS (Yes/No). If HADS depression = 'Normal' then Depression='No'. Else if HADS depression = 'Boderline abnormal' or 'Abnormal' then Depression='Yes'
- Anxiety evaluated by HADS (Yes/No). If HADS anxiety = 'Normal' then Anxiety='No'. Else if HADS anxiety = 'Boderline abnormal' or 'Abnormal' then Anxiety='Yes'
- Fatigue (FACIT-F total score) in quantitative or in classes (using quartiles), if linearity is not verified
- Global Assessment of disease activity (mm) by patient (0-no pain to 100-maxima pain imaginable) in quantitative or in classes (using quartiles), if linearity is not verified
- Global Assessment of disease activity (mm) by physician (0-no pain to 100-maxima pain imaginable) in quantitative or in classes (using quartiles), if linearity is not verified
- MATHyS global score in quantitative (only descriptive, not in the model due to collinearity with cognition score)
- Positive Anti-CCP (Yes/No)
- Positive rheumatoid factor (Yes/No)

5.2. ANALYSIS POPULATIONS

Descriptive analyses will be performed on the ITT population. Primary and secondary analyses will be done on ITT population.

For the primary analysis, the sensitivity analyses will be conducted in reproducing the same analyses, using the PPS.

Secondary efficacy analyses will be performed on the PPS, only if PPS represents less than 90% of the ITT population.

Exploratory analyses to search some patients' profiles at baseline will be performed on the ITT population. Safety analyses will be performed on the safety set (SAF).

5.3. STATISTICAL METHODS

5.3.1. Disposition of patients

Key information of the study will be presented (First patient first visit, last patient last visit, first patient last visit, last patient last visit, number of centers with at least one patient included, enrollment duration (months)^{DD}).

Disposition of patients will be depicted for patient status and patient analysis populations. The total number of patients for each of the following categories will be described:

- Enrolled patients

- Patients failed to be enrolled and the reason for non-enrollment
- Safety population
- ITT population
- Per-Protocol population.

Summary tables and flowcharts will present the number and percentage of subjects who not entered in the study and reason for non-enrolment into the registry will be presented overall (non-compliance with inclusion / exclusion criteria, patient's refusal of consent).

Summary tables and flowcharts will present the number of subjects at each assessment and the number of subjects by population. Follow-up duration^{DD} (weeks) will be calculated overall. The number and percentage of subjects who withdrew from the study and the reasons for premature withdrawal will be presented overall (adverse event, death, treatment inefficacy, major protocol deviations, consent withdrawal, lost to follow-up or other reason). Time between baseline and premature withdrawal^{DD} (weeks) will also be presented.

5.3.2. Analyses of evaluation variables

5.3.2.1. Descriptive analysis

Descriptive statistics of all data collected in the CRF and which are not considered as primary, secondary or exploratory endpoint will be provide. These data are defined in the section 5.1.1. A frequency table of the number and percentage of subjects will be provided for medical and surgical history by System Organ Class (SOC) and Preferred Term (PT) overall. A frequency table of the number and percentage of subjects will be provided for prior and concomitant treatments at baseline by therapeutic class (ATC).

5.3.2.2. Primary efficacy analysis

The primary study objective is to describe the effect of sarilumab on the variation of the total [RAID](#) score from baseline to V5 (W24). Mean change from baseline (V2) of the total [RAID](#) score to W24 (V5) will be provided with its bilateral 95% CI.

Change from baseline in total [RAID](#) score after 24 weeks will be provided using a mixed model repeated measurement. This model includes total [RAID](#) score at baseline as covariate, and interactions between the covariate and visit.

SAS code:

```
Proc MIXED;  
Class Visit;  
Model RAID_score_change= Visit + Raid_score_baseline*Visit;  
Repeated Visit / type=UN sub=id;  
Run;
```

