## 6 STUDY DESIGN

### 6.1 DESCRIPTION OF THE STUDY

This is a national, multicenter, open-label, single-arm phase IV study designed to assess the effect of sarilumab on patient-reported impact of disease, using the rheumatoid arthritis impact of disease (RAID) questionnaire, in patients with moderately to severely active RA and inadequate response or intolerance to current csDMARD or TNF inhibitors.

Four study periods are defined for this study:

- Screening period: within 28 days prior to study treatment start (Baseline visit, Day 1), out-patient eligibility is determined at the Screening visit. At Baseline visit, patient's inclusion in the study will be established.
- 6-month core period: patients who fulfil the enrolment criteria will start the investigational medicinal product (IMP), SC injection of sarilumab 200 mg every 2 weeks as monotherapy and/or in combination with methotrexate (MTX) or other csDMARD (at investigator's discretion) for 24 weeks. Patient visits are scheduled at Baseline, W4, W12, and W24.
- Long-term extension period: all patients who will complete the 6-month-core-period will be allowed to continue the treatment with sarilumab, every 2 weeks for a maximum of another 24 weeks or until the commercial availability of sarilumab, depending whichever comes first. Patient visits are scheduled every 12 weeks over the LTE period (at W36 and W48).
- Post-treatment follow-up: each patient will have one follow-up visit, between 2 and 4 weeks after his/her last administration of sarilumab.

Around 140 patients enrolled in 35 university hospital and general hospital centers are expected throughout mainland France.

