## 11 STATISTICAL CONSIDERATIONS

### 11.1 DETERMINATION OF SAMPLE SIZE

The primary study objective is to assess the change in RAID score from baseline to W24. A sufficient precision (half-length of the 95% confidence interval) is required. According to the literature (44, 45, 46) and findings from the MONARCH and TARGET studies (22, 33), the standard deviation (SD) of the RAID score could be estimated at 2.5 points. On this basis, a sample size of 140 patients (122 evaluable, if 20% non-evaluable patients) produces a precision, two-sided 95% confidence interval (CI), with a distance from the mean to the limits that will be less than 0.5 when the estimated SD is 2.5. Table below gives the 95% CI of change from baseline to W24 of RAID score with this precision (0.44), assuming that the change from baseline will be from 30% to 50% (MCII defined by Dougados in 2012; 47) of baseline score.

Expected change from baseline to W24 of RAID score (Relative to baseline %)	RAID score at Baseline	Expected change from baseline to W24 of RAID score (Absolute value)	95% CI (precision =0.5)
30%	65	2,0	[1,5 ; 2,5]
	5	1,5	[1,0 ; 2,0]
	3,5	1,1	[0,6 ; 1,6]
50%	6,5	3,3	[2,8 ; 3,8]
	5	2,5	[2,0 ; 3,0]
	3,5	1,8	[1,3 ; 2,3]

*Note that on MONARCH study (22), the % of change from baseline was 49.6% (3.32/6/69) and in TARGET study (33) 47.4% (3.24/6.83).*

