#### **11.4.2 Analyses of efficacy endpoints**

##### **11.4.2.1 Analysis of primary efficacy endpoint**

The primary study objective is to assess the change in RAID score from baseline to W24. The number of available data, mean, standard deviation, median and range (minimum, maximum) will be provided with the 95% confidence interval of mean change from baseline to W24. Main analysis will be done on ITT population. Sensitivity analysis will be conducted in reproducing the same analysis using the per-protocol population.

In addition, multivariate analyses such as ANCOVA (Analyze of Covariance), Logistic Regression and Multiple Correspondences analysis can be performed from baseline in order to exploratory explain different profiles of patients. The details of these analyses will be described on the statistical analyses plan before database frozen.

In case of any event mentioned below, the last available endpoint before the considered event will be taken in account (for RAID score for primary endpoint and for all other secondary endpoints):

- Lack of efficacy
  - More than one glucocorticoid infiltration per articulation
  - Dose increase of an ongoing glucocorticoid or start of systemic glucocorticoid treatment
  - Change in NSAID due to lack of efficacy or adverse event considered as related to treatment by the investigator
- Missing data
  - Treatment discontinuation due to lack of efficacy or adverse event (except for AEs due to NSAID). For all other cases, missing data will not be replaced.

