### **11.4.2.3 Multiplicity considerations**

Not applicable: all analyses are descriptive without test.

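### The primary endpoint has two unranked estimators, and an interval taken from the baseline-adjusted one would overstate precision for the population mean change

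*SAP*

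**What the plan says.** Protocol 11.4.2.1 defines the primary analysis as descriptive: summary statistics of the change in RAID "will be provided with the 95% confidence interval of mean change from baseline to W24". It mentions ANCOVA only as an optional exploratory tool for patient profiles. Protocol 11.1 sizes the trial on that interval: "A sufficient precision (half-length of the 95% confidence interval) is required". Protocol 6.1 describes an "open-label, single-arm phase IV study", and Protocol 11.4.2.3 says of multiplicity: "Not applicable: all analyses are descriptive without test".

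SAP 5.3.2.2 first repeats the mean change to W24, which "will be provided with its bilateral 95% CI". It then says that the W24 change will come from a repeated-measures mixed model with baseline RAID by visit as covariate, and prints the code: "Model RAID_score_change= Visit + Raid_score_baseline*Visit", with an unstructured covariance across visits. The code has no LSMEANS or ESTIMATE statement. Nothing says which result is primary or how the two relate. SAP 1.6 lists changes from the protocol to the analysis sets, a subgroup, compliance and adverse event tables, but not this model.

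**The concern.** The main result of this trial is one mean with one 95% CI. The plan offers two routes to it and leaves the choice open. They need not use the same patients. Under SAP 6.4, missing values other than those after specified discontinuations are not replaced, so the raw mean needs a W24 value, while the model also uses patients who have only W4 or W12.

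The model's output is also left to the programmer. As printed, the code gives no W24 mean. The natural completion is LSMEANS for Visit, evaluated at the sample-mean baseline. That standard error treats the mean baseline as a known constant. In a randomised comparison this does little harm, because both arms are evaluated at the same baseline value and it drops out of the difference. With one arm there is no difference to take, and the omitted variance belongs to the quantity being reported.

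**Working it through.** **Inputs from the documents.** The SD is 2.5: Protocol 11.1 says "the standard deviation (SD) of the RAID score could be estimated at 2.5 points" and applies that value to the change. Evaluable patients number 122 in Protocol 11.1 and SAP 1.4, and at least 112 in the protocol synopsis (140 × 0.8 = 112). The interval is two-sided 95%.

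**Input assumed.** ρ, the correlation between baseline RAID and the change to W24, is not in the documents. A range is shown. Some correlation is expected because the change contains baseline.

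**The plan's own figure.** Half-width = 1.96 × 2.5 / sqrt(122) = 0.444, which reproduces the stated 0.44. At n = 112 it is 1.96 × 2.5 / sqrt(112) = 0.463. This formula uses the full SD of the change, so it targets the population mean change.

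**The model at the sample-mean baseline, complete data.** Every visit has its own intercept and slope and the covariance is unstructured, so the W24 part of the model equals an ANCOVA at W24. A least-squares line passes through the means, so the point estimate equals the raw mean change. Only the standard error differs:

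- variance of the raw mean: σ²/n
- variance reported by the model: σ²(1 − ρ²)/n
- omitted, from sampling of baseline: ρ²σ²/n

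The half-width is therefore multiplied by sqrt(1 − ρ²). Coverage of the population mean change is 2Φ(1.96 × sqrt(1 − ρ²)) − 1. With n = 122 and σ = 2.5:

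| assumed abs. ρ | factor | half-width | coverage |
|---|---|---|---|
| 0 | 1.000 | 0.444 | 95.0% |
| 0.3 | 0.954 | 0.423 | 93.8% |
| 0.5 | 0.866 | 0.384 | 91.0% |
| 0.6 | 0.800 | 0.355 | 88.3% |

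**Simulation, complete data.** Settings were n = 122, change SD 2.5, equal SD at all visits, correlation 0.7 between post-baseline visits and 6,000 trials per setting. At ρ = −0.59, −0.50 and −0.39 the model's half-width was 0.360, 0.387 and 0.412, with coverage 88.7%, 91.3% and 93.1%. The raw interval had half-width 0.447 and coverage 94.7% to 95.5%.

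**Simulation, missing data.** Settings were 140 enrolled, 20% missing W24 at random, half of these also missing W12, and 1,500 trials per setting. At the same values of ρ the model gave 0.358, 0.387 and 0.421, with coverage 89.4%, 91.6% and 93.5%. The raw interval was about 0.467, with coverage 95% to 96%. At ρ = −0.50 the ratio of model to raw half-width is 0.387/0.447 = 0.866 without missing data and 0.387/0.467 = 0.829 with it. The extra narrowing is information from W4 and W12 and is legitimate.

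**The case against.** **Only one interval is promised.** SAP 5.3.2.2 states one CI, in the sentence that repeats the protocol's raw mean change; the model sentence promises none. This stands. A reader might infer that the SAP plans two intervals, one of which under-covers. The text does not go that far. What it supports is that the model's role and output are undefined, and that its most natural completion has the weakness shown.

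**Conditioning on covariates is ordinary practice.** This also stands: for the mean change conditional on the observed baselines, coverage is nominal. The SAP does not say which target it means. The sizing formula uses the unconditional SD, so the population mean change is what the trial was planned around.

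**The precision target.** A reader might also infer that the narrower interval would let the half-width target of less than 0.5 appear met when it is not. At the planned SD the documents do not support this: the raw half-width is already 0.44 to 0.46 (0.47 at n = 112 with a t quantile). To exceed 0.5, the SD of the change would have to be above 0.5 × sqrt(122)/1.96 = 2.82, or 2.70 at n = 112. That is possible if 2.5 is really a cross-sectional SD and the baseline–W24 correlation is low, but the documents give no such correlation.

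**The consequence is limited.** No test or decision rule uses the interval. The half-width difference is about 0.02 to 0.09 points over |ρ| 0.3 to 0.6, against expected changes of 1.1 to 3.3 in Protocol 11.1. This is a fair limit on the seriousness of the point.

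**Conclusion.** The point holds in a limited form. From the text alone: two estimators of the primary endpoint are unranked, the model is an undeclared addition to the protocol's analysis, and its W24 estimate, reference baseline and interval are unspecified.

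The precision loss is conditional. It arises if an interval is taken from the model at the sample-mean baseline and read as an interval for the population mean change. It is then about 1 point of coverage at |ρ| = 0.3, 4 at 0.5 and 7 at 0.6, with half-widths 5%, 13% and 20% too short for complete data. The size rests on a correlation that the documents do not give, and it is zero at ρ = 0. What is at stake is overstated precision of the trial's main result, not a wrong conclusion.

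**What to change.** In SAP 5.3.2.2, name the raw mean change to W24 with its 95% CI as the primary result. That agrees with Protocol 11.4.2.1 and with the interval on which the trial was sized.

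If a mixed model is kept as supportive:

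- use the RAID score at V2 to V5 as the response, Visit as the only fixed effect and an unstructured covariance;
- add an ESTIMATE statement with the CL option for W24 minus baseline.

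With complete data this returns the raw mean change and a standard error that includes the sampling of baseline. With missing W24 values it keeps the gain from W4 and W12. List the added model in SAP 1.6.

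The cost is a few lines of text and code and no new data. The downside is a slightly wider interval than the baseline-adjusted one.
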